Table 2: Biometric and health behavior measures before and after the intervention (N=39)

	Baseline	Week 12	P value
Weight, kg (SD)	91.6 (15.9)	89.7 (16.6)	< 0.0001
Servings of fruit per day (SD)	1.7 (1.0)	2.9 (2.1)	0.013
Servings of vegetables per day (SD)	1.9 (1.2)	2.6 (1.4)	0.009
Fruits and vegetables as snacks ^a (SD)	2.4 (0.9)	3.0 (0.8)	0.001
Regular soda drinks ^b (SD)	1.6 (0.7)	1.3 (0.4)	0.003
Fruit drinks, punch, or sports drinks ^c (SD)	1.7 (0.8)	1.5 (0.6)	0.10
Total MET-minutes per week ^d (SD)	2689.5 (3230.8)	6595.1 (7371.6)	0.02
Systolic blood pressure, mm Hg (SD)	133.9 (16.9)	127.2 (15.8)	0.001
Diastolic blood pressure, mm Hg (SD)	81.0 (9.5)	75.8 (9.6)	< 0.0001
Waist circumference, cm (SD)	102.3 (13.7)	100.6 (12.3)	0.14
Glucose, mg/dL (SD)	90.4 (18.4)	91.9 (11.1)	0.73
Total Cholesterol, mg/dL (SD)	205.1 (49.4)	190.8 (50.1)	0.02
Triglycerides, mg/dL (SD)	206.1 (175.0)	130.1 (78.6)	0.001

^a4-point Likert scale of frequency in response to, "Do you eat fruits and vegetables as snacks?"

^b4-point Likert scale of frequency in response to, "Do you drink regular soda?"

^c4-point Likert scale of frequency in response to, "Do you drink fruit drinks, punch, or sport drinks?"

^dEnergy expended from carrying out physical activity as measured by the International Physical Activity Questionnaire

Study Design and Procedures

Aim #1: Conduct a randomized trial to assess the efficacy of a social network-informed CBPR-derived health promotion intervention on obesity and other measures of cardiovascular risk in two immigrant communities.

Overview. The first aim address stages II-III of established methods for behavioral intervention research.¹¹⁰ Using a stepped wedge cluster randomized design, 60 social network-based groups (30 Hispanic, 30 Somali; each group with approximately 7 participants) will be randomly assigned (stratified by ethnicity, HP sex, and network size) to receive the intervention either immediately (step 1) or after a delay of one year (step 2). Outcomes, measured at baseline, 6 months, 12 months, and 24 months, will be derived from the American Heart

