Diffusion and contamination measurement. Network interventions broadly work through social diffusion of behavior change through social networks.⁷¹ Diffusion can also be conceived as contamination if it occurs from an intervention group network into a control group network.¹⁶⁸ Indeed, randomized controlled trials of social network interventions tend to underestimate intervention effects because of contamination.^{71,169,170} To assess the potential impact of contamination on the evaluation, we will measure diffusion of content to the intervention group and control (contamination) group through methods outlined by Simmons, et al.¹⁶⁹ We will assess whether specific terminology associated with the intervention modules were recognized by network participants in both groups. Recognition of negative control terms (health promotion terms not associated with the intervention or with obesity/weight loss) will also be assessed in both groups for comparison. The difference between diffusion of intervention terms and negative control terms in both groups (intervention and control) will provide a measure of diffusion in both groups and therefore contamination in the control group.

Measurement protocol and staff training. Participants from individual social networks will be measured in the same time-frame with the HP organizing times and locations. The measurement team will consist of one or two language/culture-concordant study assistants and the study coordinator. The study assistants will be responsible for administrating the dietary recalls and the questionnaire. The study coordinator will be responsible for overseeing biometric measures.

Randomization & Sample Size Considerations

Randomization

The units of randomization will be social network subgroups. Randomization will occur after all HPs and their social network participants are enrolled and baseline measures are completed. Randomization will be stratified according to ethnicity (Hispanic or Somali), age, and sex of the HPs as well as group size.

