Social network sub-groups are sufficiently discrete for randomization: Our social network data analysis determined that these communities were composed of enough discrete sub-groups for randomization. An example of this is that the Hispanic network had 144 unique sub-groups. When considering only sub-groups composed of five or more individuals, there were still 88 sub-groups identified using modularity calculations. This is a sufficient number of sub-networks for randomization, especially when considering the approximately equal number of Somali networks. Therefore, the high clustering observed in our preliminary data, as demonstrated by the high modularity of the networks, indicates that there are clearly distinct subgroups in the networks and that randomization via subgroups is feasible and appropriate for the study.

Sample size considerations

Stepped wedge cluster randomization trials typically have more statistical power than other cluster randomized designs.¹¹⁵ This is because each cluster is able to serve as its own control, accounting directly for the within cluster correlation of outcomes. In addition, the impact of intra-cluster correlation on power is typically smaller than on conventional cluster randomized trials.¹⁷¹ For the current study, we expect each HP to recruit 6 to 8 participants, so assume 7 per cluster and a substantial loss to follow up of 20% over 12 months. We assume a conservative intra-cluster correlation in outcomes of 0.10 to calculate the design effect DE_{sw} based on the formula:^{115,171}

$$DE_{sw} = \frac{1 + \rho(ktn + bn - 1)}{1 + \rho \left(\frac{1}{2}km + bn - 1 \right)} \cdot \frac{3(1 - \rho)}{2t \left(k - \frac{1}{k} \right)}$$

where $k = 2$ is the number of steps (including baseline), $b = 1$ is the number of measurements per subject in the baseline step, $t = 1$ is the number of measurements per subject at each step, and $n=7$ is the number of subjects per cluster. Assuming 80% follow up and equal

distribution across clusters, and a 80% power, we estimate the detectable standardized effects (SDs) for a range of numbers of enrolled HPs with a maximum probability of a Type II error of 0.05.

SD	HPs	N total
0.1	478	1673
0.2	120	420

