0.3 53 187 For the primary endpoints, a third standard deviation (0.3SD) difference between groups will be considered clinically meaningful.¹⁷² On the basis of the previous Healthy Immigrant Families study, we will assume a 0.1 standard deviation change in the control group ("contamination") so this represents a 0.4SD change in the intervention group. Therefore, the study will accrue 54 clusters (27 per group) with approximately seven participants in each cluster, for a total sample size of approximately 378 network participants.

Data Analysis

All analyses will be appropriate for stepped wedge trials. In the direct effects model, the co-primary endpoints will be changes in BMI and waist circumference from baseline to month 12 and the 12-month change in the Ajzen TPB, the common outcome for C2DREAM. We will use mixed effects regression models to adjust for correlations within social network clusters and over time.¹¹⁴ Models will include indicators for intervention status, step, and their interaction. Covariates indicated above including demographics (e.g., sex, years since arrival to the US) and social covariates will be included in profile analysis models to assess the sensitivity of the primary analysis conditional on these potential concomitant (mediating) influences. All secondary endpoints will be analyzed using the same methods as used for the primary endpoints.

Missing data will be handled in several ways using an extensive library of macro procedures designed specifically for such tasks by the Mayo Clinic Division of Biostatistics.¹⁷³ Simple imputation methods such as minimum, average, or maximum values carried forward will be followed by multiple imputation methods to assess the robustness of the study results in the presence of the missing data. All models will be assessed for goodness of fit, with effects reported with confidence intervals. All hypothesis tests will use $\alpha = 0.05$ to determine significance.

Bibliography

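### The two stratification lists differ on Health Promoter age, and the primary model leaves out the stratification factors and does not reconcile its change-from-baseline endpoint with baseline as a step

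*Combined protocol and SAP*

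**What the plan says.** **Allocation.** The Randomization section states: "Randomization will be stratified according to ethnicity (Hispanic or Somali), age, and sex of the HPs as well as group size". The Aim #1 Overview, under Study Design and Procedures, says groups are randomised "stratified by ethnicity, HP sex, and network size". Both are current text about one randomisation. Neither gives categories for age or size. Baseline is measured before randomisation.

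**Primary model.** Data Analysis says "the co-primary endpoints will be changes in BMI and waist circumference from baseline to month 12", adds a 12-month theory-of-planned-behaviour (TPB) measure, and calls for mixed models allowing for correlation within clusters and over time. The fixed effects are given in one sentence: "Models will include indicators for intervention status, step, and their interaction". Demographic and social covariates enter only sensitivity models. The section opens with "All analyses will be appropriate for stepped wedge trials" and carries the approach over: "All secondary endpoints will be analyzed using the same methods as used for the primary endpoints".

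**Meaning of step.** In the Overview, step labels the arm: groups are assigned "to receive the intervention either immediately (step 1) or after a delay of one year (step 2". Under Sample size considerations, step is a period: k = 2 "is the number of steps (including baseline".

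**The concern.** Two things looked wrong. First, the allocation factors are stated in two ways, and the primary model uses none of them. Stratified allocation makes the arms more alike on those factors; a model that ignores this reports a standard error that is, if anything, too large. HP age, HP sex and group size are not named anywhere in the analysis text. Ethnicity could enter through the participant-level demographics, but only in sensitivity models.

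Second, the endpoint definition and the model sentence allow more than one treatment of baseline. One wastes a little of the information in a baseline measured before allocation; another uses it fully. At stake are some precision, mainly for waist, and an analyst's choice that should be closed before outcome data are seen. Because the secondary endpoints use the same methods, the ambiguity carries over to them.

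**Working it through.** The plan states no figure on this point, so there is none to reproduce.

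**1. The two lists.** Assume two levels per factor, since the documents give no cut-points. The Overview list has 3 factors: 2³ = 8 strata, or 54/8 = 6.8 clusters per stratum (60/8 = 7.5 at the 60 groups in the Aims). The Randomization list has 4 factors: 2⁴ = 16 strata, or 54/16 = 3.4 (60/16 = 3.75). The lists give materially different schemes.

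**2. What the model sentence can estimate.** Take intercept, period indicators, status, and status × period.

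| Visits | Status varies over time | Status = arm |
|---|---|---|
| 0 and 12 months | rank 3 of 4 | rank 4 of 4 |
| 0, 6 and 12 months | rank 5 of 6 | rank 6 of 6 |

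With time-varying status, the lost column is the treated-at-baseline cell, which is empty by design. With two visits the interaction therefore duplicates status. With month 6 included, it separates the month-6 from the month-12 effect. With status as arm everything is estimable, but each arm has its own baseline mean.

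**3. Waist: correlation from Table 2.** Inputs: SDs 13.7 and 12.3, difference 102.3 − 100.6 = 1.7, p = 0.14, n = 39. Assume a paired t-test on all 39.
- t(38) for p = 0.14 is 1.507.
- SD of change = 1.7 × √39 / 1.507 = 7.04.
- r = (13.7² + 12.3² − 7.04²) / (2 × 13.7 × 12.3) = 0.859.
- Fisher 95% interval: 0.745 to 0.924.

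**4. Waist: precision given up.** With equal SDs, the change score has variance 2(1 − r) and the baseline-adjusted or common-baseline estimate 1 − r². The proportional cut is (1 − r)/2.
- r = 0.859: 7.1% of variance, about 4% of the SE.
- r = 0.924 to 0.745: 3.8% to 12.8% of variance, about 2% to 7% of the SE.

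With 20% missing at random at month 12, all baselines kept and clustering ignored:
- common baseline mean: (1 − r²)/0.8 = 0.328;
- separate means: (1 − r²)/0.8 + r² + 1 − 2r = 0.348;
- cut: 5.7%.

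With clustering, use the plan's ICC of 0.10, 7 × 0.8 = 5.6 people per cluster, and an assumed cluster autocorrelation (CAC) of 0.8, 0.9 or 1.0. Then R = (0.1·CAC + 0.9·IAC/5.6) / (0.1 + 0.9/5.6), with the individual autocorrelation (IAC) set so that total r = 0.859. R = 0.840, 0.872 and 0.903; (1 − R)/2 = 8.0%, 6.4% and 4.8%. That is worth 54 × (1/0.920 − 1) = 4.7 clusters down to 54 × (1/0.952 − 1) = 2.7.

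**5. BMI, with pilot weight standing in.** SDs 15.9 and 16.6, difference 1.9, p < 0.0001. The same steps give r ≥ 0.987. The cut is at most 0.7% with equal SDs, or 3.1% at the pilot SDs.

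**6. Omitted strata.** Assume the factors explain half of the persistent cluster variance and affect level only. For a change score they cancel, so the SE penalty is 0%. For a common-baseline mixed model the variance is v₁ − c²/v₀, where v₀ and v₁ are the cluster-mean variances at baseline and month 12 and c is their covariance. With CAC 0.8–1.0 and IAC 0.7–0.95, the SE penalty is 0.2% to 1.4%. If the factors predict change, the documents give no basis for a figure.

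**The case against.** The strongest reply is that baseline is largely dealt with. The endpoint is defined as a change from baseline, the sample-size section counts baseline as a step, and the analyses must suit a stepped wedge. Together these favour time-varying status with baseline as a period, where the loss is nil. That much stands: a reader might infer that the plan says nothing about baseline, and the documents do not support that. What remains open is which estimator the model sentence means, since step is the arm in one section and a period in another.

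A reader might also infer that the interaction is redundant and should go. That holds only with baseline and month 12 alone. The plan also measures at month 6, and dropping the interaction with month 6 in the model would average the effect over months 6 and 12, although the Measures section names month 12 as the primary endpoint.

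A third inference, that leaving out the strata biases the effect or inflates false positives, is not supported; the error runs the other way. Nor does the mismatch mean that the allocation cannot be verified, since the randomisation record would show it. The Randomization section is the dedicated text and the Overview a passing mention, so the mismatch may be editorial.

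The precision figures are fairly called thin. They come from one rounded p-value in a 12-week, single-arm, four-group pilot, and the same back-calculation gives negative correlations for glucose, fruit servings and MET-minutes. Taking the pilot waist SDs at face value would give about 20% (1 − 12.3²(1 − r²)/7.04²), but the fall from 13.7 to 12.3 is compatible with noise (Pitman–Morgan t(37) = 1.28, p = 0.21), so that figure should not be used.

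**Conclusion.** The point stands as a specification gap of modest size. The lists conflict on HP age and must be reconciled. The primary model omits the stratification factors, which is conservative rather than biasing: about 0–1.4% of the SE if half of the persistent cluster variance is explained and the factors affect level only. For baseline, the loss is nil under time-varying status with a common baseline mean. Under separate baseline means it is about 7% of variance for waist (roughly 4–13%; about 6% with 20% missing at month 12; 5–8% with clustering at the central r) and at most 1–3% for BMI. These figures assume that 12-week pilot correlations carry to 12 months. None can be given for the TPB measure or the Life's Simple 7 composite. The case for acting rests less on the precision gained than on settling the model in advance at almost no cost.

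**What to change.** - Reconcile the two lists to the one actually used, with its categories for size and, if used, age.
- Include those factors as fixed effects in the primary and secondary models.
- Define intervention status and step as used in the model.
- Either adjust for the baseline value of the outcome, or use a repeated-measures model with a common baseline mean; if the latter is already intended, say so.
- State that the primary contrast is the month-12 effect. Keep the status-by-period interaction when month 6 is in the model, noting that the treated-at-baseline cell does not exist.
- Leave the demographic and social covariate models as sensitivity analyses.

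Cost: a decision on the list and a few sentences in Data Analysis. At two levels per factor, three or four factors use 3–4 of about 52 cluster-level degrees of freedom (54 clusters less 2 arms). No new data are needed, because baseline is already measured before randomisation.

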Association's "Life's Simple 7": BMI and waist circumference, blood pressure, fasting blood glucose, total cholesterol, physical activity level, and dietary quality. We will also measure quality of life and potential mediators of treatment effect consistent with our theoretical framework. The intervention will consist of community-based mentoring and education sessions, group activities, and application of a community toolkit for healthy weight loss delivered by trained HPs from Hispanic and Somali communities to their social networks. During the control period, participants will receive printed health information developed by the study team during each assessment that is not directly related to diet or weight loss.

Figure 1. Study Design and Intervention Schedule

Month	0	0	0-5	6	6-11	12	12-18	18-23	24
Intervention Group	Baseline Measures	Randomization	12 peer-led, face-to-face or virtual group-based sessions • Goal setting • Tracking of physical activity and diet • Educational content • Positive reflections	6-Month Measures	12 peer-led, face-to-face or virtual group-based sessions • Goal setting • Tracking of physical activity and diet • Positive reflections	12-Month Measures	Sustainability Phase No Organized Intervention	Sustainability Phase No Organized Intervention	24-Month Measures
			No Intervention		No intervention		12 peer-led, face-to-face or virtual group-based sessions • Goal setting • Tracking of physical activity and diet • Educational content • Positive reflections	12 peer-led, face-to-face or virtual group-based sessions • Goal setting • Tracking of physical activity and diet • Positive reflections	

Blinding. Study staff performing measurements and data analysis as well as all named investigators will be blinded to treatment condition.

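### The 80% power is calculated for a three-period stepped wedge, but the month-12 primary endpoint is a parallel cluster comparison with a baseline, and power for that contrast is not derived

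*Combined protocol and SAP*

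**What the plan says.** Under Sample size considerations, the trial is sized with a stepped-wedge design effect with k = 2, b = 1 and t = 1. The efficiency argument is "This is because each cluster is able to serve as its own control, accounting directly for the within cluster correlation of outcomes". The other inputs are seven participants per cluster, "a substantial loss to follow up of 20% over 12 months", and "We assume a conservative intra-cluster correlation in outcomes of 0.10 to calculate the design effect". The target includes "distribution across clusters, and a 80% power". The table lists 53 clusters at 0.3 SD, and the plan accrues 54.

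Under Data Analysis, "the co-primary endpoints will be changes in BMI and waist circumference from baseline to month 12"; the Measures section also marks month 12 as the primary time point. The Overview assigns groups "to receive the intervention either immediately (step 1) or after a delay of one year (step 2". Figure 1 shows no intervention in the delayed arm until month 12. For the immediate arm, months 12 to 24 are labelled "Sustainability Phase No Organized Intervention".

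Data Analysis also says that analyses will suit a stepped wedge design, with terms for intervention status, step and their interaction. It does not say which visits enter the primary model.

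**The concern.** With k = 2, b = 1 and t = 1 the design effect counts b + kt = 3 measured periods, ending with every cluster treated. Part of its gain comes from seeing each cluster both untreated and treated. At month 12 no delayed cluster has been treated, so the stated endpoint compares 27 clusters with 27 in parallel, each with a baseline. The formula cannot be adapted to that case: one post-baseline step means k = 1, and the term k − 1/k becomes zero.

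The 24-month visit does not plainly supply the missing period, because the immediate arm is by then a year past its last organised session. The loss allowance also stops at 12 months.

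A null month-12 result could be read as coming from a trial with 80% power when no such power has been shown for that comparison. The two designs also respond differently to the ICC. Above 0.10 the stepped-wedge design effect falls, while the parallel one keeps rising.

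**Working it through.** **Inputs.** 54 clusters, equal allocation; 7 × 0.8 = 5.6 followed per cluster; ICC 0.10; 0.3 SD; 80% power (all from Sample size considerations). Alpha is from Data Analysis: "All hypothesis tests will use $\alpha = 0.05$ to determine significance". Two-sided testing is assumed. The sample-size text also gives a Type II error of 0.05, which conflicts with 80% power; I take the 80%. The symbol printed as km in the denominator is read as ktn.

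**1. The plan's own figure.** The unadjusted total is 4 × 7.849 / 0.09 = 348.8. At n = 5.6:

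- DE_sw = [1 + 0.10 × (11.2 + 5.6 − 1)] / [1 + 0.10 × (5.6 + 5.6 − 1)] × [3 × 0.90 / (2 × 1.5)] = (2.58 / 2.02) × 0.90 = 1.150.
- Clusters needed: 348.8 × 1.150 / 5.6 = about 72. With no loss (n = 7, DE 1.174) it is 58.5. The table says 53, which does not reproduce.
- Power at 54 clusters: SE = √(4 × 1.150 / (54 × 5.6)) = 0.1233; 0.3 / 0.1233 = 2.43; Φ(2.43 − 1.96) = **68%**. With no loss it is 77%.

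**2. Parallel contrast, 0.3 SD and ICC on the change scale.**

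- DE = 1 + 4.6 × 0.10 = 1.46.
- SE = √(4 × 1.46 / 302.4) = 0.139; 0.3 / 0.139 = 2.16; power = Φ(0.20) = **58%**.
- Detectable effect at 80% power: 2.802 × 0.139 = 0.39 SD. Clusters needed for 0.3 SD: about 91.

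**3. Parallel contrast with baseline adjustment, under the formula's own variance model** (a constant cluster effect and no further within-person correlation).

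- Variance of a cluster mean: 0.10 + 0.90 / 5.6 = 0.2607. Covariance of baseline and month-12 means: 0.10.
- Correlation of cluster means: R = 0.10 / 0.2607 = 0.384, so 1 − R² = 0.853.
- SE = 0.139 × √0.853 = 0.128; power = Φ(2.34 − 1.96) = **65%**.

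**4. Splitting the gap.** From 80% to 68% is about 12 points, because the table does not follow from its formula. From 68.2% to 64.7% is 3.5 points, or from 68.2% to 57.9% about 10 points, because of the design.

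**5. If 0.3 SD is the SD of the measured level.** Let r be the individual baseline-to-month-12 correlation (not given in the plan), with the cluster effect constant over time. The covariance of cluster means is 0.10 + [(r − 0.10) / 0.90] × 0.90 / 5.6.

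| r | R (cluster means) | 1 − R² | SE | Baseline-adjusted power |
|---|---|---|---|---|
| 0.3 | 0.52 | 0.729 | 0.119 | 72% |
| 0.5 | 0.66 | 0.568 | 0.105 | 82% |
| 0.7 | 0.79 | 0.369 | 0.084 | 94% |

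**6. Sensitivity to the ICC (n = 5.6, change scale for the parallel power).**

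| ICC | DE_sw | Parallel DE | Parallel power |
|---|---|---|---|
| 0.05 | 1.13 | 1.23 | 65% |
| 0.10 | 1.15 | 1.46 | 58% |
| 0.20 | 1.09 | 1.92 | 47% |

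**The case against.** A reader might infer that using the wrong design effect takes power from 80% to 58%. The documents do not support that, for two reasons. Most of the fall on either parallel calculation comes from the table not matching its own formula, which is a separate fault. And 58% is not fixed by the stated inputs: it needs both 0.3 SD and the ICC to describe the change score. The plan speaks of correlation in outcomes and of changes of 0.1 and 0.4 SD, which can equally mean change in units of the outcome's own SD.

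On that second reading power may be ample. The pilot waist result (change 1.7 cm, n = 39, p = 0.14) implies a change SD of about 7.0 cm and, with SDs of 13.7 and 12.3, r of about 0.86 if the test was a paired t-test. These are 12-week, single-arm data, so they only suggest the direction. This objection stands, and it rules out a flat claim that the trial is underpowered.

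The analysis wording also leaves room for a stepped-wedge model that uses 24-month data, so it cannot be said that post-crossover data are certainly excluded. But the endpoint is defined to month 12, and the plan does not say how later data would contribute to it.

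Finally, a reader might infer that calling an ICC of 0.10 conservative is an error. It need not be: the word can simply mean a value set above the one expected, which is valid for a parallel design too. What does not carry over is the stepped-wedge formula's insensitivity to the ICC.

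**Conclusion.** The concern holds in this form: the 80% power at 0.3 SD with 54 clusters is not derived for the month-12 primary contrast, because the design effect belongs to a three-period stepped wedge and that contrast ends before crossover. The cost of the mismatch is about 3.5 points if baseline is used under the formula's own variance model, and about 10 points on the change scale. Both are measured from the 68% that the printed formula supports, not from 80%.

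These figures assume two-sided 5%, equal allocation, 5.6 followed in every cluster and a normal reference. On the level scale the conclusion about adequacy may reverse, depending on r. So the finding is that primary-endpoint power is unestablished, not that it is known to be too low.

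**What to change.** In Sample size considerations and Data Analysis:

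- State that the primary contrast is the month-12 parallel comparison, and list the visits that enter the primary model, reconciling this with the stepped-wedge wording.
- State whether 0.3 SD and the ICC are on the change or the level scale.
- For the primary endpoint, replace DE_sw with DE = 1 + (m − 1) × ICC, m = 5.6. If baseline is a covariate on the level scale, multiply by (1 − R²), where R is the baseline-to-month-12 correlation of cluster means, not of individuals.
- Restate power or detectable effect at the planned number of clusters, over ICC 0.05, 0.10 and 0.20 (change scale at 54 clusters: 65%, 58%, 47%) and over a stated range of r. Settle the number first: the Overview gives 60 groups, which on the change scale at ICC 0.10 gives 62%.
- Do not use the own-control argument, or the stepped-wedge formula's insensitivity to the ICC, as support for primary-endpoint power. Keep a stepped-wedge power statement only for an analysis that uses the 24-month data.

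The cost is one recalculation and a rewritten paragraph. The restatement itself adds no participants or visits. The downside is that the stated power becomes less favourable on the change-scale reading.

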Using a stepped wedge cluster randomized design, 60 social network sub-groups of adults (30 Hispanic, 30Somali) with approximately 480 participants (approximately 7 per group) will be randomly assigned to receive the intervention either immediately or after a delay of one year. The intervention will consist of 12 community-based mentoring and education sessions and group activities, followed by 12 maintenance sessions delivered by trained Somali and Hispanic interventionists to members of their groups in a face-to-face or virtual format. Outcomes measured at baseline, 6 months, 12 months, and 24 months, will be derived from the American Heart Association's "Life's Simple 7": BMI and waist circumference (primary outcomes), blood pressure, fasting blood glucose, total cholesterol, physical activity level, dietary quality, and health-related quality of life. We will also test potential mediators of treatment effect consistent with the C2DREAM conceptual model.

The expected product will be a CBPR-derived, social network-informed intervention to reduce cardiovascular risk among two immigrant groups. The proposed study is innovative; it will be the first to evaluate a social network health promotion intervention among immigrant populations. Given that over one million immigrants arrive in the US annually, the potential public health impact of this work is considerable.

Preliminary Data

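### The 53 clusters (adopted as 54) for 0.3 SD do not follow from the printed formula and inputs, and the trial size is given both as 54 clusters/378 and as 60 groups/about 480

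*Combined protocol and SAP*

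**What the plan says.** All references are to the combined protocol and SAP.

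- **Sample size considerations, inputs.** The plan prints a stepped-wedge design effect with intra-cluster correlation 0.10, k = 2, b = 1, t = 1 and n = 7. On recruitment and loss it says "so assume 7 per cluster and a substantial loss to follow up of 20% over 12 months". The power is given in the phrase "distribution across clusters, and a 80% power", and the same sentence ends "with a maximum probability of a Type II error of 0.05".
- **Sample size considerations, table.** At 0.1, 0.2 and 0.3 SD the plan needs 478, 120 and 53 health promoters (one per cluster), with 'N total' of 1673, 420 and 187.
- **Effect and target.** "a third standard deviation (0.3SD) difference between groups will be considered clinically meaningful". From this the plan concludes that "the study will accrue 54 clusters (27 per group) with approximately seven participants in each cluster". It puts the resulting enrolment at 378 people, give or take.
- **Data Analysis.** Tests use alpha 0.05, with sidedness not stated. Change from baseline to month 12 in BMI and in waist circumference are among the co-primary endpoints.
- **Specific Aims.** 60 sub-groups (30 Hispanic, 30 Somali) "with approximately 480 participants (approximately 7 per group").
- **Study Design and Procedures, Overview.** "60 social network-based groups (30 Hispanic, 30 Somali; each group with approximately 7 participants").

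**The concern.** The accrual target is presented as the consequence of the table, so the table should follow from the formula and inputs beside it. It does not, and the discrepancy affects every row.

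Two trial sizes also stand in current text. As written, a reader cannot tell whether recruitment is complete at 54 or at 60 groups, or what power either size has at 0.3 SD under the stated assumptions. Two labels add to the difficulty: a Type II error of 0.05 cannot accompany 80% power, and a total of 187 cannot sit beside 53 clusters of 7 (53 × 7 = 371).

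**Working it through.** **1. How the plan's figures appear to arise.** A two-sided t-test at 0.05 with 80% power needs 1571, 394 and 176 per arm at 0.1, 0.2 and 0.3 SD. Multiply by 1.065:

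- 1571 × 1.065 = 1673
- 394 × 1.065 = 420
- 176 × 1.065 = 187

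That is the whole 'N total' column, so it behaves as a per-arm count. Doubling for two arms and dividing by 7 gives 478, 120 and 53.4, the cluster column. Then 187/7 = 26.7, rounded up to 27 per arm, gives 54 clusters, and 54 × 7 = 378.

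**2. The printed design effect.** The denominator contains a symbol m that is not defined. I read the term as ½ktn, treating m as tn.

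DE = [1 + 0.1(14 + 7 − 1)] / [1 + 0.1(7 + 7 − 1)] × 3(0.9) / [2(2 − ½)] = (3.0/2.3) × 0.9 = 1.174.

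With 20% loss, 7 × 0.8 = 5.6 people are retained per cluster. Putting n = 5.6 into the formula gives 1.150. Including loss, the total multiplier is 1.150/0.8 = 1.44 to 1.174/0.8 = 1.47. The table implies about 1.065.

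**3. Clusters required.** The unadjusted total is 4(1.96 + 0.8416)²/d², which is 348.8 at 0.3 SD.

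- No loss: 348.8 × 1.174/7 = 58.5, so 59
- 20% loss, DE at n = 5.6: 348.8 × 1.150/5.6 = 71.6, so 72
- 20% loss, DE at n = 7: 348.8 × 1.174/5.6 = 73.1, so 74

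A one-sided test (unadjusted total 274.8) gives 47 without loss and 57–58 with it. None of these is 53 or 54.

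**4. All rows are affected.** Clusters × d² should be constant down the table, and it is: 478 × 0.01 = 4.78, 120 × 0.04 = 4.80, 53 × 0.09 = 4.77. The printed inputs, two-sided, give 5.27 without loss and 6.44–6.58 with it. The whole table is offset, which points to different inputs and not to a slip in one row.

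**5. What the formula gives for the stated sizes.** Power = Φ[(d/2)√(C × r/DE) − 1.96], with C clusters, r people analysed per cluster and d = 0.3. For 54 × 7 after loss, 54 × 5.6 = 302.4. Then √(302.4/1.150) = 16.22, and Φ(0.15 × 16.22 − 1.96) = 0.68. For 60 × 8, 6.4 are retained and DE is 1.164–1.188.

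| Size | Power after 20% loss | Power, no loss | Effect detectable with 80% power after loss |
|---|---|---|---|
| 54 × 7 = 378 | 67–68% | 77% | 0.345–0.35 SD |
| 60 × 7 = 420 | 72–73% | 81% | 0.33 SD |
| 60 × 8 = 480 | 77–78% | – | 0.31 SD |

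The ranges reflect DE at the retained or the full cluster size.

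**6. The two sizes.** 54 × 7 = 378 agrees with itself. 60 × 7 = 420, not 480; a total of 480 needs 480/60 = 8 per group.

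**The case against.** **The formula may have been misread from the PDF.** Reading m as tn is an assumption. But to reach a multiplier of 1.065 without loss, with n = 7 elsewhere, 2.7/[1 + 0.1(m + 6)] = 1.065 requires m of a little over 9. With loss, a DE of 1.065 × 0.8 = 0.852 requires m of about 15.7. Neither is a quantity that the plan defines. The objection limits the precision of the recomputed figures but does not rescue 53.

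**Sidedness, power and effect size can be worked out.** This largely stands. All three rows fit a two-sided test with 80% power, so the Type II wording is evidently a slip for Type I and does not mean that 95% power was intended. The effect is 0.3 SD: that is the table row, and the contamination sum (0.1 + 0.3 = 0.4 SD) works only with it. The words for one third do not create a second target.

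**60 exceeds 54, and 8 per group lies within the expected 6 to 8 recruits.** Both are true, so the larger size is not below the plan's own calculation. Still, the Specific Aims sentence pairs 480 with about 7 per group. No text presents the larger number as over-recruitment, and 20% loss is already listed as an input to the calculation.

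**The trial may be adequately powered.** A reader might infer from the table above that it is underpowered. The documents do not support that. The printed formula contains no within-person correlation, although 12-month change is the endpoint. They also do not say whether the SD is that of the raw value or of the change. Actual power could be higher or lower.

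**Conclusion.** The point holds. The table and the 54-cluster target drawn from it do not follow from the printed formula and inputs: 53 is stated, against 59 without loss or 72–74 with the plan's own 20% loss. At 0.3 SD, two-sided after loss, none of the stated sizes (54 × 7, 60 × 7 or 60 × 8) reaches 80% under that formula. Without loss, 60 × 7 does and 54 × 7 does not.

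This rests on reading m as tn, a normal approximation, and two-sided alpha, which the plan does not state but which its table fits. It shows that the sizing statement is not reproducible, not that the trial lacks power.

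Separately, 54/about 378 and 60/about 480 are both operative and unreconciled, and 480 does not agree with 60 groups of about 7. The two label slips are minor. Nor should 187 be read as the intended enrolment: it appears to be a per-arm figure, and the adopted total of 378 is consistent with that.

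**What to change.** 1. Recompute the table from the printed formula with 5.6 retained per cluster, or print the formula and inputs that produced 478/120/53. Include any within-person correlation, the handling of loss, and what the SD refers to. Define or correct the denominator symbol.
2. State that alpha is two-sided, change Type II to Type I, and relabel 'N total' as per arm.
3. Give one target in Specific Aims, the Overview and Sample size considerations: clusters, measured participants per cluster, and total. Say whether 27 per group means trial arm or ethnic group.
4. Restate the power at 0.3 SD, or the detectable effect, for that size after the assumed loss.

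The cost is protocol wording and one recalculated table. No added enrolment is required, though the stated power may become less favourable.
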